Place-Based Mapping in EAS Listeners

NCT04722042

Modified Date: 2/17/2025

Statistical Power and Design

For the first experiment under Aim 1, we plan to investigate monaural speech for EAS users listening with a place-based versus a default map. We plan to recruit 40 subjects from the UNC Adult CI Program (~140 surgeries/year) at initial activation (~2-4 weeks postop). Inclusion criteria are 18-65 years of age, MED-EL array recipient, and a postoperative unaided detection threshold of ≤ 65 dB HL at 125 Hz. Recruitment is limited to recipients of one manufacturer to control for number and separation of electrodes, as well as coding strategy. Subjects will be fit with the Sonnet2EAS device. Subjects must identify English as their native language since test materials are in English. Subjects will be excluded if they report or present with a cognitive delay or impairment, as indicated with the Mini Mental State Examination (Folstein, Folstein, & McHugh; 1975). Subjects will be randomized into one of 2 groups: 1) default map, or 2) place-based map. In addition to these 40 CI users, age-matched NH listeners will be recruited for reference.

Monaural speech perception will be compared between groups over the study period (activation, and 1, 3, 6, & 12 mos). Subjects will be evaluated with the alternative map at the initial activation and 12-mo intervals for within-subjects comparisons. The tester will be blinded to map condition to limit bias. Test measures include: CNC word recognition in quiet, AzBio sentence recognition in noise (10 dB SNR), and vowel recognition. Word and sentence recognition will be assessed in the sound field, at one meter from the speaker. Recorded materials will be presented at 60 dB SPL, and masking will be delivered to the contralateral ear via an insert phone when warranted. Vowel recognition is essential for speech perception and is sensitive to changes in low-to-mid frequency representation in EAS simulations. Vowel recognition will be assessed using the English Vowel Recognition Test from TigerSpeech Technology®, a tool that assesses recognition of 12 vowel sounds, presented in a /h-/vowel-/d/ context. The EAS device will be connected to the computer via a direct-connect cable. The subject will listen to the target and select the perceived vowel from a closed-set list, with responses scored in percent correct; confusion matrices are also provided. An age-matched, NH control group will complete the CNC and AzBio tests while listening to EAS simulations of the default and place-based maps based on parameters characterizing stimulation for individual CI subjects; NH listeners are tested only once.

Dependent measures are vowel recognition, word recognition in quiet, and sentence recognition in noise. Linear Mixed Models (LMM) will be used to assess the main effects of group (default vs place-based) and interval (activation, 1, 3, 6, & 12 mos), and the interaction between group and interval on each measure, with a significance criterion of $\alpha=0.05$. Aided acoustic audibility as measured with the Speech Intelligibility Index (SII) will be included as a within-subjects variable to control for differences in residual hearing. Subject demographic data to be reported include: gender, age, unaided thresholds, AID of the most apical electrode, and mismatch. Mismatch will be quantified as the absolute semitone deviation at 1500 Hz (~267° using the SG function), which has been shown to be an important region for frequency alignment in vocoder simulations. Reduced models will assess the main effects of map (default vs place-based) and interval (activation & 12 mos), and the two-way interaction for the within-subjects comparison. Results from the NH control group will be compared to EAS users at activation, to corroborate effects of mapping approach in the findings from the CI subjects.

For Aim 2, we plan to investigate the binaural hearing abilities of EAS users listening with a place-based map versus a default map. We plan to recruit 24 subjects from the experiments under Aim 1 with thresholds ≤ 65 dB HL at 125 Hz in the contralateral ear. For NH subjects listening to a bilateral CI simulation, SRM is ~8 dB (95% CI: ~7 dB) with no interaural mismatch and ~4 dB (95% CI: ~11 dB) with an interaural mismatch of 1 mm (Xu et al., 2020). Similar results are obtained with bilateral CI recipients (Hu et al., 2018). Based on these data, our experiment is powered to observe effect sizes of $d \geq 0.90$ ($\alpha < 0.05$, $1 - \beta = 0.8$).

Binaural hearing will be assessed in the soundbooth, using an 11-speaker arc spanning -90° to 90°. Subject listen with EAS+HA or EAS+NH at the 1, 3, 6, & 12-month intervals. Binaural hearing measures include: 1) spatially masked sentence recognition, 2) localization, and 3) subjective benefit. Spatially masked sentence recognition will be completed, with performance calculated as SRM_{EAS} and SRM_{Contra}. The dB SNR for each subject will be determined at the 1-month interval in the co-located condition, by decreasing the dB SNR from 10 dB to 0 dB in 5 dB steps until the subject scores <50% correct. Subjects will be evaluated at the same SNR for the subsequent intervals. Localization will be assessed by calculating the root-mean-squared (RMS) error of sound source identification using 200-ms noise bursts at varied intensity levels (52, 62, or 72 dB SPL). Subjective benefit will be assessed using the Speech, Spatial, and Qualities of Hearing Scale (SSQ;

Gatehouse & Noble, 2004), with results evaluated on the 3 subscales and 10 pragmatic subscales (defined by Gatehouse & Akeroyd, 2006).

The primary analysis is the effect of group (default vs place-based) on SRM_{EAS} , SRM_{Contra} , and localization. An LMM will assess the main effects (group and interval) and the associated interaction, with a significance criterion of $\alpha < 0.05$. Secondary analyses will include the effect of group on subjective benefit, assessed for the Spatial Hearing subscale, and relevant pragmatic subscales, including: 1) Speech in Speech Contexts, 2) Segregation of Sounds and Objects, and 3) Listening Effort.

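### Age is collected but left out of both between-group mixed models; pre-specifying it is a cheap step that may sharpen the group comparisons, by an amount the documents cannot settle

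*Combined protocol and SAP*

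**What the plan says.** All references are to the combined protocol and SAP, under Statistical Power and Design.

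- **Recruitment and allocation, Aim 1.** "We plan to recruit 40 subjects from the UNC Adult CI Program", aged 18 to 65. "Subjects will be randomized into one of 2 groups: 1) default map, or 2) place-based map". The allocation ratio is not given and no stratification is mentioned.
- **Use of age.** For the reference group, "age-matched NH listeners will be recruited for reference"; the next paragraph has these listeners complete CNC and AzBio only. For the EAS users, age appears in a descriptive list: "Subject demographic data to be reported include: gender, age, unaided thresholds, AID of the most apical electrode, and mismatch".
- **Aim 1 between-group model.** Group, interval (five time points from activation to 12 months) and their interaction, with aided audibility (SII) added to account for residual hearing. The reduced within-subject models contain map, interval and their interaction.
- **Aim 2.** "We plan to recruit 24 subjects from the experiments under Aim 1", tested at 1, 3, 6 and 12 months. For the primary analysis, "An LMM will assess the main effects (group and interval) and the associated interaction"; no covariate is named. The plan states that Aim 2 has 80% power for effect sizes of 0.90 or more at the 0.05 level.

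**The concern.** Age is already collected and cannot be altered by the assigned map, so adjusting for it cannot remove part of a map effect. The plan accepts covariate adjustment in principle, since it adjusts Aim 1 for SII. It also treats age as worth controlling when it chooses NH listeners. Yet the randomised comparisons, with about 20 and 12 subjects per group, leave age in the error term.

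Two things are at stake. If age explains part of the between-subject spread, the group effect is estimated less precisely than it could be. If the groups differ in age by chance, the planned models have no term to correct for it. In Aim 2 the first test is at 1 month, after the assigned map is in use, so no earlier SRM or localization score is available as a baseline covariate.

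**Working it through.** **Inputs from the document.** N = 40 with five visits (Aim 1); N = 24 with four visits (Aim 2); d = 0.90 and power 0.80 (stated for Aim 2 only); significance level 0.05.

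**Assumptions.** Two-sided test; equal groups; d = 0.90 borrowed for Aim 1, which states no effect size; d expressed in single-visit SDs; between-visit correlation rho from 0.2 to 0.8, or a single visit; r, the within-group correlation of age with the subject value analysed, from 0 to 0.5.

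**Formulas.** Averaging k visits multiplies the variance by V = (1 + (k - 1) x rho)/k. Adding age multiplies it by (1 - r^2)(1 + 1/(N - 4)); the second factor is the expected cost of chance age imbalance. With F the product of the factors that apply, power comes from a non-central t with noncentrality 0.90 / sqrt(F x 4/N), on N - 2 degrees of freedom without age and N - 3 with it.

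**The plan's own figure.** With 24 subjects and one value each, the noncentrality is 0.90 / sqrt(4/24) = 2.20 and power is 55.9%, not 80%. Averaging four visits at rho = 0.42 gives V = (1 + 3 x 0.42)/4 = 0.565, an effect of 0.90 / sqrt(0.565) = 1.20 and power of 80.0%. The document gives no such rho, so the starting point for Aim 2 is itself uncertain. That is a separate matter; here only the change on adding age counts.

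**Aim 2, N = 24, power in %**

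| Data used | Without age | r = 0 | r = 0.2 | r = 0.3 | r = 0.5 |
|---|---|---|---|---|---|
| One visit | 55.9 | 53.7 | 55.4 | 57.6 | 65.9 |
| Four visits, rho 0.8 | 62.8 | 60.5 | 62.2 | 64.6 | 72.9 |
| Four visits, rho 0.42 | 80.0 | 77.9 | 79.5 | 81.6 | 88.3 |
| Four visits, rho 0.2 | 91.5 | 90.0 | 91.1 | 92.5 | 96.3 |

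The change is -1 to -2 points at r = 0, +1 to +2 at r = 0.3 and +5 to +10 at r = 0.5.

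**Aim 1, N = 40, power in %**

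| Data used | Without age | r = 0 | r = 0.2 | r = 0.3 | r = 0.5 |
|---|---|---|---|---|---|
| One visit | 79.2 | 78.0 | 79.7 | 81.7 | 88.4 |
| Five visits, rho 0.42 | 96.6 | 96.2 | 96.8 | 97.5 | 99.1 |

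The change is about -1 point or less at r = 0, +1 to +3 at r = 0.3 and +2 to +9 at r = 0.5. A rho below 0.42 puts unadjusted power still nearer its ceiling and shrinks the gain further. SII is not modelled here.

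**Break-even.** Ignoring the lost degree of freedom, (1 - r^2)(1 + 1/(N - 4)) = 1 gives r = 1/sqrt(N - 3): 0.22 for N = 24 and 0.16 for N = 40. With the lost degree of freedom the values are 0.23 and 0.17.

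**Chance imbalance.** Under simple equal allocation the difference in mean age has a standard deviation of sqrt(4/N) age SDs: 0.41 for N = 24 and 0.32 for N = 40. By normal approximation it exceeds half an age SD in about 22% and 11% of trials respectively.

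**The case against.** The case for leaving the models alone is substantial.

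- **Nothing is invalid.** A reader might infer that the group comparison is biased by age. The documents do not support that: allocation is randomised, so the issue is precision and chance imbalance only.
- **Age matching is weak evidence that age matters here.** A reader might infer that the plan itself expects age to drive all its outcomes. But matching is routine for a non-randomised reference group, and the NH listeners take only CNC and AzBio. It says nothing direct about vowel recognition, SRM or localization. This stands, and it makes the support weaker for Aim 2.
- **The benefit may be nil or negative.** No age-outcome correlation is given, and below r of about 0.2 the term gains nothing or costs a little. This stands.
- **The design may already limit age effects.** SII may absorb some in Aim 1; SRM is a difference score at an individually set SNR; cognitive impairment is an exclusion; and the within-subject map comparison largely removes age. These are possible reductions in the gain, not reasons why adjustment would do harm.
- **Why age?** Unaided thresholds and electrode position are also recorded, and Aim 2 mixes listeners with a hearing aid and with normal hearing in the other ear. The documents do not show that age is the best single covariate. Its advantages are that it is already collected and that the map cannot affect it.

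A reader might also expect age adjustment to secure 80% power for Aim 2. It does not on one value per subject: even at r = 0.5 power is 65.9%.

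**Conclusion.** The point holds as an optional, low-cost improvement. Age is recorded, neither between-group model uses it, and no stratification is described, so whatever age explains stays in the error of the group effect. How much that is cannot be determined from the documents. Under the assumptions shown, the likely range runs from a loss of 1 to 2 points of power if age is unrelated to outcome, to a gain of up to about 10 points (Aim 2) or 9 points (Aim 1) at r = 0.5. The Aim 1 gain falls to about 2 points at that r if all five visits contribute at rho = 0.42. Confidence that the gain would be material is low, and lower for SRM and localization than for CNC and AzBio.

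**What to change.** In the Aim 1 analysis paragraph, pre-specify age at activation as a linear fixed covariate in the between-group model, alongside SII. In the Aim 2 primary analysis paragraph, add the same term to the model for SRM and localization. Report each model without age as a sensitivity analysis. The within-subject map models need no change. State the choice before outcome data are compared by group, so that adjustment cannot be decided on the results.

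The cost is a sentence in each analysis paragraph and one degree of freedom per model. If age proves unrelated to outcome, the expected loss is about 1 point of power with 40 subjects and about 2 with 24. No new data, visits or subjects are needed.

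### The Aim 1 within-subject models leave out the assigned map, so pooling the groups mixes a year's experience into the 12-month map effect and its error

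*Combined protocol and SAP*

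**What the plan says.** All of this stands in the Combined protocol and SAP, under Statistical Power and Design, in the Aim 1 paragraphs.

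- Design: "Subjects will be randomized into one of 2 groups: 1) default map, or 2) place-based map". The planned number is 40; the allocation ratio is not given.
- Procedures: "Subjects will be evaluated with the alternative map at the initial activation and 12-mo intervals for within-subjects comparisons". Each subject therefore contributes four scores per measure to the within-subject comparison: two maps at two visits.
- Between-group analysis: "Linear Mixed Models (LMM) will be used to assess the main effects of group (default vs place-based) and interval", together with their interaction. The assigned map is a factor here.
- Within-subject analysis: "Reduced models will assess the main effects of map (default vs place-based) and interval (activation & 12 mos), and the two-way interaction". The assigned map is not a factor here.

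The text does not say whether the within-subject models pool the two randomised groups or are fitted in each group. It gives no random-effects structure, and no power or effect size for this comparison.

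**The concern.** At activation neither map is familiar, so the place-minus-default difference means the same thing in both groups. At 12 months it does not. Subjects assigned to the place-based map have had a year with it, and subjects assigned to the default map have had a year with that one. The plan does not describe daily use in so many words, but it compares the groups through 12 months and treats the other map as the alternative, so this is the natural reading.

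A pooled model with only map and interval cannot tell the effect of the map from the effect of being used to it. Three things are at stake:

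- the 12-month map estimate may be biased;
- its standard error is too large even when it is not biased;
- the map × interval term can sit near zero although every subject has gained on the assigned map, and a reader could take that as no effect of experience.

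**Working it through.** **What is estimated.** Let M be the map effect (place-based minus default). Let E_P and E_D be the 12-month gains on the assigned map, over the unfamiliar one, in the place-based and default groups. Let nP and nD be the numbers completing. The interval term takes up only the gain common to both maps.

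| | Place-based group | Default group |
|---|---|---|
| Place minus default, activation | M | M |
| Place minus default, 12 months | M + E_P | M − E_D |
| Map × interval (M stable) | E_P | −E_D |

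Pooled, the 12-month map effect estimates M + (nP·E_P − nD·E_D)/(nP + nD), and map × interval estimates the second part alone. This is algebra and needs no assumed value. Both are free of experience only if nP·E_P = nD·E_D. The group × map × interval term, which is not in the model, estimates E_P + E_D.

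Fitted by group, the 12-month map effect alone is still mixed with experience, but map × interval separates the two if M is stable. What is then missing is a joint test across groups.

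**Inputs for size.** The 40 subjects and alpha of 0.05 are from the plan. The rest is assumed: 20 per group, a two-sided test, a random intercept for subject (SD 15 points), a within-subject difference with SD 10 points (residual variance 100/2 = 50), and equal gains F. The plan has no figure of its own to reproduce.

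**Precision with equal groups and equal gains.** The pooled model leaves ±F/2 in each subject's two 12-month scores, a sum of squares of F²/2 over 3 within-subject degrees of freedom.

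- Residual variance = 50 + F²/6 = 66.7, 87.5, 116.7 for F = 10, 15, 20.
- SE ratio = √(1 + F²/300) = 1.15, 1.32, 1.53; at F = 5 it is 1.04. In general it is √(1 + F²/(3·SD²)), so only F/SD matters.
- 12-month SE = √(2 × variance/40) = 1.83, 2.09, 2.42 points, against √(2 × 50/40) = 1.58.
- The true sampling SD stays 1.58, so the difference detectable with 80% power is 1.98 × SE + 0.842 × 1.58 = 4.9, 5.5, 6.1 points, against 4.5.

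Simulation with 20,000 trials per row:

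| F | Power, M = 4, 12 months: as listed | With group terms | Type I error as listed (M = 0) | Pooled map × interval significant | Group × map × interval significant |
|---|---|---|---|---|---|
| 5 | 67.4% | 70.5% | – | – | 60.2% |
| 10 | 58.6% | 70.0% | 2.4% | 2.5% | 99.4% |
| 15 | 46.0% | 71.0% | 1.0% | 0.9% | 100% |
| 20 | 30.6% | 70.4% | 0.3% | 0.3% | 100% |

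For the map main effect over both visits, power is 89.5%, 82.3% and 69.7% at F = 10, 15, 20, against 94.0% to 94.5% with group terms. In 100 mixed-model fits at F = 15, the 12-month SE was 2.10 as listed, 2.10 with only a group main effect added, and 1.58 with group × map × interval.

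**Bias.**

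- Unequal completers, 18 and 14, equal gains: (18F − 14F)/32 = F/8 = 1.25, 1.9, 2.5 points for F = 10, 15, 20. Simulated means were 1.24, 1.86 and 2.49 as listed and about 0 with group terms averaged equally. Rejection under M = 0 stayed near 6%, because the SE is inflated.
- Unequal gains, 15 and 5, 20 per group, M = 0: (20 × 15 − 20 × 5)/40 = 5.0 points, rejected in 80% of 4,000 simulated trials. The equally weighted average with group terms is also 5.0.
- Gains of 5 and 15 with M = 5: 5 + (20 × 5 − 20 × 15)/40 = 0, so a real map effect is hidden.

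**The case against.** The strongest reply is that the harm depends on pooling, and the text does not say that the groups are pooled. Reduced models, in the plural, could mean one per group or one per measure. That stands: what is certain is an unspecified choice and a missing term, and the by-group reading does much less damage.

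Second, the loss of power rests on an assumed F/SD. At F/SD = 0.5 the SE grows only 1.04 fold, and with SD 15 and F = 10 it grows √(1 + 100/675) = 1.07 fold. That also stands; the loss is a few percentage points when the gain is small beside the paired SD. The random intercept is assumed too. A simple paired analysis at 12 months with F = 10 would have SE √((100 + 100)/40) = 2.24, larger than 1.83. The calculations also leave out the audibility index, which the plan names for the preceding model and does not mention for the reduced ones.

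Third, group terms do not cure the bias from unequal gains. True: they remove the part due to unequal numbers and make the rest visible. Unequal gains cannot be dismissed, since the trial itself asks whether the two maps lead to different results over time.

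Fourth, the randomised comparison is sound. Also true. It is a separate analysis, however, and does not repair this one.

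**Conclusion.** The concern holds, on the condition that the groups are pooled. The within-subject models as listed then give a 12-month map effect and a map × interval term that both carry (nP·E_P − nD·E_D)/(nP + nD), and a residual that absorbs the rest of the experience effect. The direction and the formula do not depend on assumed values; the sizes do.

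With equal completers and equal gains the harm is lost power, not false positives: on the assumptions above the SE rises 1.04 to 1.53 fold as the gain goes from half to twice the paired SD. With unequal gains the 12-month estimate is off by half the difference in gains when the groups are equal in size.

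The activation comparison and the randomised group × interval model are not affected. This is a worthwhile and cheap improvement to an additional analysis, not a threat to the trial's main comparison.

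**What to change.** State whether the within-subject models are pooled or fitted by group, and state the random-effects structure. If pooled, add assigned map (group), group × interval, group × map and group × map × interval, with subject as a random effect. A group main effect alone does not help. Then report:

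- the map effect at activation;
- the 12-month map effect separately by assigned group;
- the average of those two, weighted equally, with a note that it equals the pure map effect only if the gains on the two maps are equal and otherwise carries (E_P − E_D)/2;
- the assigned-versus-alternative contrast at 12 months, which averages M + E_P and −M + E_D and so estimates (E_P + E_D)/2.

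If the models are fitted by group, say so and add a joint test across groups.

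The cost is one or two sentences of analysis text and no new data. With 40 complete subjects, within-subject degrees of freedom go from 160 − 40 − 3 = 117 to 114.

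### Aim 2 takes 24 subjects from the randomised Aim 1 cohort without fixing when or how they enter, and neither stratifies nor adjusts for contralateral hearing

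*Combined protocol and SAP*

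**What the plan says.** All of this stands in the protocol and SAP under Statistical Power and Design.

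- **Aim 1, recruitment and allocation.** "We plan to recruit 40 subjects from the UNC Adult CI Program (~140 surgeries/year) at initial activation (~2-4 weeks postop" gives the size and time of entry. Then: "Subjects will be randomized into one of 2 groups: 1) default map, or 2) place-based map". No ratio, block size or stratification factor is stated. The hearing criterion is "a postoperative unaided detection threshold of ≤ 65 dB HL at 125 Hz"; the contralateral ear is not mentioned for Aim 1.
- **Aim 1, testing.** "Subjects will be evaluated with the alternative map at the initial activation and 12-mo intervals for within-subjects comparisons", so subjects in both groups hear both maps at activation. On masking the plan says "The tester will be blinded to map condition to limit bias"; it does not say whether subjects are masked.
- **Aim 2, source of subjects.** "We plan to recruit 24 subjects from the experiments under Aim 1 with thresholds ≤ 65 dB HL at 125 Hz in the contralateral ear". No time of entry is given, and no rule for choosing if more than 24 qualify.
- **Aim 2, testing.** "Subject listen with EAS+HA or EAS+NH at the 1, 3, 6, & 12-month intervals". There is no activation test, and two kinds of contralateral listener are combined.
- **Aim 2, analysis.** "The primary analysis is the effect of group (default vs place-based) on SRM_{EAS} , SRM_{Contra} , and localization". The mixed model contains group, interval and their interaction. No covariate is named, whereas the Aim 1 model includes aided audibility (SII).

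**The concern.** The Aim 2 primary comparison draws its validity from the Aim 1 randomisation. A subset of a randomised cohort keeps that protection if membership is fixed by something the allocation cannot influence. The plan supplies half of this condition, a threshold in the other ear. It does not say that all eligible subjects enter, or that participation is settled before the subject has heard a map.

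Two things are at stake. If entry is optional and follows map use, willingness to take part could differ by assigned map, and no planned analysis addresses that. Separately, contralateral hearing plausibly bears on spatial release from masking (SRM) and localisation. With 24 subjects, and neither stratification nor adjustment, chance differences between groups in that factor add noise to all three primary outcomes.

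**Working it through.** **Inputs.** From the plan: 40 subjects in Aim 1, 24 in Aim 2, planning effect d = 0.90, α = 0.05, power 0.80. Assumed: 1:1 allocation, a two-sided two-sample t-test at one visit, 6 to 10 normal-hearing (NH) contralateral ears among the 24, and the refusal pattern in step 4.

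**1. Yardstick.** Noncentrality is d × √(n₁n₂/(n₁+n₂)) on 22 degrees of freedom.

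- 12:12: 0.90 × √(144/24) = 2.20, power 0.559
- 10:14: 0.90 × √(140/24) = 2.17, power 0.547
- 9:15: 0.90 × √(135/24) = 2.13, power 0.532

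The plan's 0.80 is not reproduced under this simple test. It would be roughly met by averaging four visits with a correlation of about 0.4 (power 0.81), which the plan does not state. That is a separate question. Here only the differences between splits matter: 0.559 − 0.547 = 0.012 and 0.559 − 0.532 = 0.027.

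**2. Split of the 24 without stratification.** With 20:20 among the 40, the number in one arm is hypergeometric (40, 20, 24), SD 1.57.

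- P(14:10 or worse) = 0.333
- P(15:9 or worse) = 0.105
- Average power 0.552, against 0.559 for a forced 12:12

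Under simple randomisation, binomial (24, ½), the two probabilities are 54% and 31%, and average power is 0.541. Stratification on eligibility alone therefore recovers about 1 to 2 points on average, and 1 to 3 points in the 14:10 and 15:9 cases.

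**3. Imbalance in contralateral status.** If K of the Aim 2 subjects have an NH ear, the number in one arm is hypergeometric (40, 20, K). The probability that the groups differ by 4 or more such subjects is:

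- K = 6: 0.182
- K = 8: 0.235
- K = 10: 0.273

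These figures include the variation in arm size from step 2.

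**4. Selection, if it occurs.** Suppose that in one arm only the fraction p least satisfied with the map declines, and that satisfaction correlates ρ with the outcome. That arm's mean shifts by ρ × φ(z_p)/(1 − p) SD.

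| p | ρ = 1 | ρ = 0.5 | Share of d = 0.90 at ρ = 0.5 | Type I error at ρ = 0.5 |
|---|---|---|---|---|
| 0.10 | 0.1755/0.90 = 0.195 | 0.10 | 11% | 5.6% |
| 0.20 | 0.2800/0.80 = 0.350 | 0.17 | 19% | 6.9% |
| 0.30 | 0.3477/0.70 = 0.497 | 0.25 | 28% | 9.0% |

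Type I error is for 12 per arm, two-sided. A shift of 0.50 SD would give 21.6%. A shift of zero, which the documents equally allow, leaves 5%.

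**The case against.** A reader might infer that Aim 2 subjects have already been randomised and have lived with their map when they are asked to join. The documents do not show this. They give no entry time; a first binaural test at 1 month fixes the test schedule, not the moment of agreement. One agreement at activation covering both aims fits every sentence, and since consent pages are not in the public text, their absence proves nothing. This objection stands. What remains is that the design text does not state the condition that would protect the comparison.

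The eligibility rule does not itself break randomisation, because the map in one ear is not expected to change the 125 Hz threshold in the other. That stands too: bias needs entry after map use, discretion over entry, and refusal that differs by arm. Similar refusal in both arms would largely cancel. Hearing both maps at activation is weak evidence of a preference, since the plan does not say that subjects are told which is which.

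It would also be too strong to say that a selected subset could not be examined. Aim 1 gives word, sentence and vowel scores at activation, and thresholds, SII, mismatch and age. These allow a partial check of entrants against non-entrants by arm, although none is a binaural measure.

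Chance imbalance is not bias, and the nominal error rate already covers it. The stratification argument is therefore one of precision, and for arm sizes alone the gain is small.

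Finally, the plural reference to Aim 1 experiments might suggest that non-randomised subjects could enter Aim 2. No other Aim 1 experiment is described, and Aim 2 compares the same two groups, so that reading lacks support.

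**Conclusion.** The concern holds as a gap in specification with a modest precision cost, not as demonstrated bias. The plan leaves open when Aim 2 participation is settled, which eligible subjects enter, and how contralateral hearing is handled.

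- **Selection.** Possible only under discretionary entry after map use. Its size is unknown; the shifts of 0.10 to 0.25 SD, with type I error of about 6% to 9%, rest entirely on assumed one-arm refusal of 10% to 30% and a correlation of 0.5.
- **Arm sizes.** A 14:10 or worse split has a 33% chance under 20:20 allocation, but costs only about 1 to 3 power points in the cases computed.
- **Contralateral status.** This is the larger precision concern. The 18% to 27% chance of a difference of 4 or more depends on the assumed 6 to 10 NH ears and on 1:1 allocation.

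The change is worth making because it is cheap and protects a primary comparison. Confidence is medium, since the actual order of enrolment steps is not in the documents.

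**What to change.** 1. Determine contralateral eligibility and Aim 2 participation at the activation visit, before randomisation and before any map is heard.
2. Enter all eligible randomised Aim 1 subjects consecutively until 24 is reached.
3. Stratify the Aim 1 allocation by Aim 2 eligibility and contralateral status: not eligible, eligible with a hearing aid, eligible with a normal-hearing ear. Use small blocks.
4. Include contralateral status as a covariate in the Aim 2 mixed model.
5. For subjects already randomised, add the covariate, report by assigned map how many were eligible, approached and declined, and compare entrants with non-entrants on the Aim 1 activation data.

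**Cost.** No added subjects. One threshold is measured, and Aim 2 participation sought, earlier, at a visit that already takes place. With 40 subjects in three strata, overall balance may be off by a subject or two. The model loses one degree of freedom.

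### The Aim 2 claim of 80% power for d ≥ 0.90 with 24 subjects does not follow from the inputs the plan states

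*Combined protocol and SAP*

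**What the plan says.** All of this is in the combined protocol and SAP, under Statistical Power and Design.

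- **Design.** In Aim 1, "Subjects will be randomized into one of 2 groups", default map or place-based map. No allocation ratio is given.
- **Aim 2 sample.** "We plan to recruit 24 subjects from the experiments under Aim 1", restricted by a hearing threshold in the contralateral ear.
- **Power.** The Aim 2 text cites spatial release from masking (SRM) of about 8 dB without interaural mismatch and about 4 dB with a 1 mm mismatch, with 95% CI figures of about 7 and 11 dB. It continues: "Based on these data, our experiment is powered to observe effect sizes of" d ≥ 0.90, at alpha below 0.05 and power 0.8.
- **Aim 2 visits.** "Subject listen with EAS+HA or EAS+NH at the 1, 3, 6, & 12-month intervals".
- **Aim 2 analysis.** "The primary analysis is the effect of group (default vs place-based) on" SRM on the EAS side, SRM on the contralateral side, and localization. The model is a linear mixed model (LMM) with group, interval and their interaction.

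The power sentence gives d, alpha and power. It does not give sidedness, group split, the SD that standardises d, the correlation between visits, or an allowance for loss.

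**The concern.** A power statement for Aim 2 should describe the Aim 2 primary contrast, which is a between-group comparison of 24 people. A d of 0.90 looks too small for that sample: the simplest two-group calculation falls well short of 80%. The cited SRM means and spreads could inform d, but they contain no between-visit correlation, so they cannot show what the four visits add.

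This is the only power figure in the document. If Aim 2 finds no significant group effect, the reader needs to know which effect the study could have detected. As written, that could be anything from well below 0.90 to about 1.20.

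**Working it through.** **Inputs from the plan:** N = 24; d = 0.90; alpha = 0.05; target power 80%; two randomised groups; four visits. **Assumed:** 12 per group, which is the most favourable split (10/14 gives 54.7% two-sided, 8/16 gives 51.1%). Both one-sided and two-sided tests are shown because the plan does not say which applies.

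**1. Trying to reproduce 80% with one value per subject.** Two-sample t test, df = 12 + 12 − 2 = 22, noncentrality = d × √(n₁n₂/(n₁+n₂)) = 0.90 × √6 = 2.20.

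| | Two-sided | One-sided |
|---|---|---|
| Critical t | 2.07 | 1.72 |
| Power at d = 0.90 | 55.9% | 68.8% |
| d detectable with 80% power | 1.20 | 1.05 |
| n per group for 80% at d = 0.90 | 21 (81.2%) | 16 (80.0%) |

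The stated 80% is not reproduced.

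**2. Four visits.** With complete data, the group effect averaged over visits is a t test on subject means. If d is on the single-visit SD and r is the average correlation between pairs of visits, the variance of a subject mean is (1 + 3r)/4 times the single-visit variance, so the effective effect is 0.90/√((1 + 3r)/4). At r = 0.5, for example, the factor is 0.625 and the effective effect is 0.90/0.791 = 1.14.

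| r | Factor | Power at d = 0.90, two-sided / one-sided | Detectable d at 80%, two-sided / one-sided |
|---|---|---|---|
| 0.3 | 0.475 | 86% / 93% | 0.82 / 0.72 |
| 0.5 | 0.625 | 76% / 85% | 0.95 / 0.83 |
| 0.7 | 0.775 | 67% / 78% | 1.05 / 0.92 |

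The three correlations are illustrative; the plan supports none in particular. Power at d = 0.90 is exactly 80% at r ≈ 0.42 two-sided or 0.65 one-sided, and any higher correlation gives less. If one subject per group is lost (11/11), the limits fall to about 0.35 and 0.56. If the correlation instead decays by visit order, with adjacent-visit correlation p, the average is (3p + 2p² + p³)/6, and the limits correspond to p ≈ 0.57 and 0.76. Simulation of 200,000 trials per setting agreed; compound symmetry at 0.5 gave 75.9% two-sided and 85.4% one-sided.

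**3. Other routes to 80%.**

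- *Paired comparison.* Twelve subjects, with d on the SD of differences, give 81.0% two-sided. The plan does describe switching maps: "Subjects will be evaluated with the alternative map at the initial activation and 12-mo intervals for within-subjects comparisons". But that directly follows "Monaural speech perception will be compared between groups over the study period" in Aim 1, and the Aim 2 text describes only a group comparison.
- *Covariate.* "Aided acoustic audibility as measured with the Speech Intelligibility Index (SII) will be included as a within-subjects variable" is said of the Aim 1 model; the Aim 2 model names no covariate. With one df lost, a covariate would have to explain about 44% of the variance of a single value for 80% two-sided (26% one-sided). For subject means, the two-sided requirement is about 10% at r = 0.5 and 27% at r = 0.7. One-sided, it is nil at r = 0.5 and about 5% at r = 0.7.
- *The full Aim 1 sample.* At 20/20, one value per subject, power is 79.2% two-sided. That is close to 80%, but it is not the Aim 2 sample, and the match does not prove where the figure came from.

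**4. The cited SRM data.** The difference is 8 − 4 = 4 dB. If 7 and 11 dB are half-widths of 95% ranges of individual values, the SDs are 7/1.96 = 3.57 and 11/1.96 = 5.61, the pooled SD is 4.70 and d = 4/4.70 = 0.85. If they are full widths, the pooled SD is 2.35 and d = 1.70. The plan does not say which reading applies, and neither gives 0.90. Either way this concerns where d comes from, not whether 24 subjects give 80% power at d = 0.90.

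**The case against.** The strongest reply is that 56% and 69% describe an analysis the plan does not propose. Aim 2 has four visits and an LMM, and the two-sided range for that model at the illustrative correlations, 86% down to 67%, contains the stated 80%. A one-sided test tolerates correlations up to 0.65. On this view nothing has been miscalculated; details are missing, and the consequence is confined to how a null result is read.

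Much of that stands. The single-value figures should not be read as the power of the planned model, and the 80% has not been disproved. It is also fair that one reading of the cited SRM data gives d near 0.85, so 0.90 may be close to the effect the investigators expect.

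The point survives because the plan says its power rests on the cited data, and those data do not contain the quantity that decides the answer. Nothing elsewhere in the document supplies that quantity, a one-sided test, or an Aim 2 covariate.

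**Conclusion.** The concern holds. The Aim 2 power statement cannot be derived from what the plan states. On those inputs alone, with an assumed 12/12 split and one value per subject, power at d = 0.90 is about 56% two-sided or 69% one-sided. The planned four-visit analysis reaches 80% only if the average between-visit correlation is about 0.42 or lower two-sided (0.65 or lower one-sided), assuming complete data, d on the single-visit SD and no covariate. The figure is unsupported, not disproved. It should be fixed because it is the document's only power figure and concerns the primary Aim 2 contrast. The validity of the group comparison itself is not affected.

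**What to change.** Restate the power sentence for the group effect in the Aim 2 LMM. Give the sidedness, expected split, SD used for d, between-visit correlation and its structure, and expected loss. For example:

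> With 12 per group, two-sided alpha 0.05, no loss and d on the single-visit SD, the group comparison has 80% power for d of about 1.20 at a single visit and, assuming compound symmetry, about 0.82, 0.95 and 1.05 for the four-visit average at within-subject correlations of 0.3, 0.5 and 0.7.

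The sponsor can keep d ≥ 0.90 by stating and justifying a correlation, sidedness or covariate that supports it. The cost is one sentence of protocol text, and the stated detectable effect may become less favourable. Enrolment, endpoints and model do not change.
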